# Data Handling

A master key will be generated during randomization. It will contain patient initials and medical record number, and a unique code. Only the primary investigator will have access to this master key which will be kept in an encrypted secure computer at Texas Tech.

A separate de-identified secure database (Redcap) using the unique code as index will be used for collection of data points. The baseline demographic data will transferred directly into the deidentified database after randomization. All collection forms /surveys will be destroyed after data is transferred into electronic database. Using the master key, we will perform a retrospective chart review to complete final data points (pathology results, return to ER, re-admissions, re-operations). All data analysis will be carried out in SPSS version 24 (IBM, Armonk, NY, USA). Continuous baseline demographic variables: (age, BMI, operating time and uterine weight) will be compared using t-student, and Chi square for categorical variables (steroid use, diabetes). Postoperative bleeding will first be evaluated as a binary categorical value, and compared using Chi Square. Inter-quartile ranges/t-student and logistic regression will be utilized to compare SF-36 results at 3 months. We will also use Chi Square to compare categorical values such as return to ER, Infection and re-admission.

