#### Secondary objectives:

Determine if there is a difference in patient satisfaction after surgery by comparing results from SF-36 questionnaire

Determine if this technique changes the rate of vaginal cuff complications (cellulitis, dehiscence, vaginal cuff hematoma, and abscess)

Evaluate the difference in operative time between techniques for this portion of the procedure.

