## Methods

Participants will be enrolled based on eligibility criteria. They will be consented to participate in the office during their preoperative visit. Baseline demographic data collected will include Age, BMI, Diabetes status, HgbA1c within the last 3 months if available, and daily steroid use. Subjects will be allocated on a 1:1 ratio via block randomization in blocks of 4. Assignment will be performed after completion of hysterectomy, before cuff closure, via a pre-generated sequential masked randomized

list. An opaque sealed envelope containing group allocation will be opened by the circulating nurse prior to vaginal cuff closure, who will communicate contents to the surgeon.

Vaginal cuff-closure will be performed by high-volume surgeons with subspecialty training in minimally invasive gynecology who have similar operating techniques. If the subject's group corresponds to "Control group", the surgeon will re-approximate the cuff in a standard fashion, using a running-barbed suture (2-0 V-LOC 90 with tapered needle), starting at the right apex, moving towards the left, and then back-tracking once to further reinforce the closure. If the allocation corresponds to "Apical stitches", surgeon will use 0 polyglactin 910 suture on a tapered needle to place figure of 8 sutures on both (left and right) apexes. Knot tying technique (intra-corporeal vs extracorporeal) will be up to surgeon preference. After this is completed, barbed suture will be used to re-approximate the remainder of the vaginal cuff from right to left, backtracking once at the end for reinforcement. Time when vaginal cuff closure starts and ends will be noted. Surgeon will also examine vaginal introitus at the end of the case, noting any lacerations.

After the surgery, a survey will be filled out by the primary surgeon (See ANNEX 1).

Immediate postoperative care and discharge criteria will be performed per unit guidelines. All patients are instructed to abstain from heavy lifting (more than 30 lbs) and vaginal penetrative sex for 6 weeks.

When patients arrive for their postoperative visit (10-20 days after surgery), a member of the research team who is blinded to allocation will give out a short survey before the patient meets the physician (SEE ANNEX 2). Remainder of visit will occur in a routine fashion.

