## Limitations

The main confounding factors when comparing surgical techniques are difference in operating style between surgeons and baseline surgical characteristics (large uteri that may require more dissection and tissue manipulation, etc.). To control for this we are only recruiting patients from 3 surgeons who have a similar operating technique. In addition to this, we are documenting operating time and specimen weight, which can be used to compare both groups and assure that they are homogenous to these potential confounders. Baseline patient characteristics that can influence postoperative healing, such as diabetes and steroid use will also be accounted for. Post-hoc analysis will also be made specifically stratifying the data based on these characteristics.

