#### Costs

Both methods of vaginal-cuff closure are routinely performed, albeit in an uncontrolled fashion, hence the cost of hysterectomies will not differ when compared to patients not undergoing a research protocol. In general, we expect that closing the apexes will add approximately 5 minutes of operating time. This will be measured during the study. The polyglactin suture is already routinely opened during hysterectomy cases. Research staff salaries are supported by the Department of Obstetrics and Gynecology at Texas Tech.

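### Operating time is tested as a baseline variable to show that the arms are alike, but it includes the randomised cuff closure, which the protocol expects to take about 5 minutes longer in one arm

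*Protocol*

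**What the plan says.** - **Data Handling** classes operating time with age, BMI and uterine weight and tests it between arms: "Continuous baseline demographic variables: (age, BMI, operating time and uterine weight) will be compared using t-student".
- **Limitations** gives the purpose: "we are documenting operating time and specimen weight, which can be used to compare both groups and assure that they are homogenous". The confounding it has in mind comes from surgical difficulty, for example "large uteri that may require more dissection and tissue manipulation". The section ends with: "Post-hoc analysis will also be made specifically stratifying the data based on these characteristics".
- **Methods** fixes when allocation happens: "Assignment will be performed after completion of hysterectomy, before cuff closure". Its own list of baseline data (age, BMI, diabetes status, HgbA1c, daily steroid use) does not include operating time.
- **Costs** predicts that allocation changes operating time: "we expect that closing the apexes will add approximately 5 minutes of operating time", followed by "This will be measured during the study".
- **Secondary objectives** treats the closure time as an outcome: "Evaluate the difference in operative time between techniques for this portion of the procedure".
- **Annex 1** records four clock times: surgery start and stop, and vaginal cuff start and stop. Cuff start is when the first suture and sewing instruments are in the abdomen; cuff stop is when the last suture is cut.

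**The concern.** A baseline comparison is informative only if the variable could not have been changed by the allocated treatment. Operating time measured from surgery start to surgery stop includes the cuff closure, which is the randomised step. The protocol itself expects that step to be longer in the apical-stitch arm and studies its duration as an outcome.

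The comparison therefore has a non-zero expected difference even when randomisation has worked perfectly. It can report an imbalance in surgical difficulty that does not exist. It can also hide a real one, if the experimental arm happened to have the easier hysterectomies and the longer closure made up the gap. Limitations offers this comparison as a safeguard against what it regards as the main confounders, so readers are likely to rely on it.

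**Working it through.** **Inputs from the protocol**
- 77 patients per arm (Sample Size). This reproduces with Kelsey's formula: (1.960 + 0.842)² × 0.125 × 0.875 × 2 / 0.15² = 76.3, rounded up to 77 per arm and 154 in total.
- Expected shift in operating time: about 5 minutes (Costs).
- Student's t-test (Data Handling). A two-sided 5% level is assumed for it.

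**Input not in the protocol**
- The standard deviation (SD) of whole-operation time. I assume 20, 30, 40 and 60 minutes to show a range.

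**Formulas**
- Standard error of the arm difference: SE = SD × √(2/77).
- Rejection rate: noncentral t with 77 + 77 − 2 = 152 degrees of freedom and noncentrality 5/SE; the critical value is 1.976.
- Chance that the experimental arm has the longer mean: Φ(5/SE).
- Observed difference needed for significance: 1.976 × SE.

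**Results for a 5-minute shift**

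| Assumed SD (min) | SE (min) | Balance test rejects | Experimental mean longer | Difference needed (min) |
|---|---|---|---|---|
| 20 | 3.2 | 33.8% | 94.0% | 6.4 |
| 30 | 4.8 | 17.7% | 84.9% | 9.6 |
| 40 | 6.4 | 12.0% | 78.1% | 12.7 |
| 60 | 9.7 | 8.1% | 69.7% | 19.1 |
| True baseline variable | – | 5% | 50% | – |

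**The flag is lopsided.** At SD 30 the threshold is 9.6 minutes. A chance imbalance in the time before closure triggers it at 9.6 − 5 = 4.6 minutes if the experimental arm is the longer one, but only at 9.6 + 5 = 14.6 minutes if it is the shorter one.

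**Sensitivity to the shift.** At SD 30, 40 and 60 the rejection rate is 9.5%, 7.5% and 6.1% for a 3-minute shift, and 30.1%, 19.0% and 11.1% for a 7-minute shift.

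**Check by simulation (40,000 trials per SD).** Rejection was 33.7%, 17.7%, 12.1% and 8.2% at SD 20, 30, 40 and 60. With skewed times (lognormal, assumed mean 120 minutes) it was 17.3%, 12.0% and 7.9% at SD 30, 40 and 60. The same data without the 5 minutes gave 4.8% to 5.0%. That last result follows by construction; it shows only that the excess comes from the closure step.

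**The case against.** **Operating time is not defined in Data Handling.** Annex 1 would allow a time before closure to be derived, and the confounder described in Limitations, dissection of large uteri, arises before the cuff. The derivation might be left to an analysis plan that is not shown. It is true that the term is undefined. But nothing in the protocol says cuff time is to be subtracted, Costs uses the term to include closure, and Annex 1 keeps surgery stop separate from the cuff times. If time before closure was intended, the same wording change is needed to say so.

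**Nothing inferential depends on it.** The primary test and sample size are untouched, no adjustment for operating time is planned, and a reader could use the recorded cuff time to explain a difference. This stands, and it is why the point is minor.

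**The stratification sentence may not cover operating time.** Its nearest antecedent is diabetes and steroid use. This is a fair reading, so I raise stratification only conditionally.

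**The size rests on an assumed SD.** Also true. The 34% belongs to the smallest SD in the table, and the same formula gives 6.7% and 6.1% at SD 80 and 100. The excess may be slight, but the expected difference is not zero at any SD.

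**The replacement interval is not strictly before randomisation.** By the Annex 1 definition it ends just after the envelope is opened, and the arms begin with different sutures. This stands as a small residual; the interval contains no stitch.

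**Conclusion.** The concern holds and is minor. The protocol presents as baseline a quantity that it elsewhere expects the allocated technique to lengthen, so the stated balance check is wrong as written.

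At 77 per arm and a 5-minute shift, the check would signal imbalance in about 8% to 34% of correctly randomised trials for SDs of 60 down to 20 minutes, and the experimental arm would look slower in 70% to 94% of them. These figures rest on the protocol's own 5-minute expectation, on an assumed SD, and on reading operating time as surgery start to stop. The damage is confined to this comparison and its interpretation. If the post-hoc stratification were meant to include operating time, that analysis would condition on a variable affected by allocation.

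**What to change.** In Data Handling and Limitations, replace operating time in the balance comparison with the interval from surgery start to vaginal cuff start. Use the same interval in the post-hoc stratification if operating time is meant to be part of it. Report whole-operation time and cuff-closure time only as outcomes. Uterine weight can stay where it is, since it is fixed before randomisation.

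The cost is wording only: both clock times are already on Annex 1 and no new data are needed. The small downside is that the interval takes in envelope opening and suture loading, which a footnote to the baseline table can state.

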## Sample Size

Sample size was calculated for primary outcome. Based on our experience when angles are not secured separately, incidence of at least mild spotting ranges around 20%. We expect the intervention to decrease this to an incidence of 5%, In order to detect the expected change with a significance level of 5% and a power of 80%, a sample of 154 patients is required (77 per group) using Kelsey's formula.

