Between 90-114 days after surgery, patients will be called by a member of the research team and given a survey regarding bleeding and quality of life (See ANNEX 3 and SF-36 survey).

A retrospective chart review will also be performed 3 months after enrollment to evaluate for any postoperative visits to the emergency department / re-admissions / re-operations / infections.

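### The protocol assigns both a t-test and logistic regression to the same 3-month SF-36 comparison, defines no binary SF-36 outcome and does not say which analysis decides

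*Protocol*

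**What the plan says.** The first secondary objective in the protocol is: "Determine if there is a difference in patient satisfaction after surgery by comparing results from SF-36 questionnaire". It asks for a comparison of questionnaire results and mentions no responder definition or threshold. Under Methods, the SF-36 is given once, in the telephone call 90 to 114 days after surgery.

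The method is in Data Handling: "Inter-quartile ranges/t-student and logistic regression will be utilized to compare SF-36 results at 3 months". The sentence just before it handles the primary outcome differently: "Postoperative bleeding will first be evaluated as a binary categorical value, and compared using Chi Square". So where the protocol means a yes/no outcome, it says so. The SF-36 gets no such label, and nothing in the protocol ranks the two SF-36 analyses.

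The Sample Size section concerns bleeding only. It states no SF-36 difference, SD or power.

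**The concern.** The two inferential tools named for this comparison need different kinds of outcome. The t-test takes the score as a number. Logistic regression, unless qualified, models a binary outcome, and none is defined. The sentence therefore cannot be carried out on its ordinary reading until someone adds a cut.

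Three things are at stake:

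- **Choice of cut.** A threshold set once the scores are visible can be chosen for its result.
- **Conflict.** One analysis may be significant and the other not, with no rule for which is reported as the answer to the objective.
- **Error rate.** Two chances at a positive finding carry more than a 5% false-positive risk.

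This goes beyond detail that a protocol may leave to its SAP. The protocol does not defer the SF-36 method. It names one, and part of what it names does not fit the outcome as described.

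**Working it through.** **1. The plan's own figure.** The protocol says "a sample of 154 patients is required (77 per group) using Kelsey's formula", for 20% against 5%, "with a significance level of 5% and a power of 80"%. Kelsey's formula, with mean proportion (0.20 + 0.05)/2 = 0.125 and two-sided 5%:

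n per arm = (1.960 + 0.842)² × 2 × 0.125 × 0.875 / 0.15² = 7.849 × 0.21875 / 0.0225 = 76.3, so 77 per arm and 154 in total.

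The stated size reproduces exactly. It does not involve the SF-36, so nothing below changes it.

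**2. Assumptions for the SF-36.** The 77 per arm comes from the Sample Size section. Normal scores with equal SD and no loss to follow-up are assumed. The true difference is set where the t-test has 80% power:

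d = (1.960 + 0.842) × √(2/77) = 0.4515 SD.

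This is a reference point, not a difference the protocol claims.

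**3. Information lost by a split.** For normal scores cut at quantile q, with c the normal quantile and φ the normal density, efficiency relative to the t-test is φ(c)² / [q(1 − q)].

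- Median: 0.3989² / 0.25 = 0.64.
- 75th percentile: 0.3178² / 0.1875 = 0.54.

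**4. Power if the split analysis alone decided.** With the cut at c + d/2, the proportions above it are 1 − Φ(c + d/2) and 1 − Φ(c − d/2). Power is Φ{[|p₁ − p₂|√77 − 1.960√(2p̄(1 − p̄))] / √(p₁(1 − p₁) + p₂(1 − p₂))}.

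- Median: 0.411 against 0.589. (1.567 − 1.386)/0.696 = 0.26, power 60%.
- 75th percentile: 0.184 against 0.327. (1.253 − 1.209)/0.608 = 0.07, power 53%.

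Simulations (20,000 trials per setting, Wald test from the logistic model) agree:

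| Cut | Normal approximation | Simulation, d = 0.452, fixed cut | Simulation, d = 0.455 |
|---|---|---|---|
| Median | 60.3% | 58.7% | 62.2% (cut at the pooled sample median) |
| 75th percentile | 52.9% | 51.9% | 52.6% |

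Most of the gap between 59% and 62% comes from whether the cut is a fixed value or the trial's own median.

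**5. Disagreement when both are run.** Same simulation, d = 0.452, fixed cut, 5% level:

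- Median: t-test only 23.0%, logistic only 2.2%, together about 25%.
- 75th percentile: 29.3% and 2.3%, together about 32%.

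**6. False positives with no true difference, counting either test:**

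- Median: 4.97% + 2.48% (logistic only) = 7.45%.
- 75th percentile: 4.96% + 2.95% = 7.91%.

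These figures use one cut fixed beforehand. A cut chosen from the data would add to them.

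**7. A form that needs no cut.** With arm as the dependent variable and the score as predictor, logistic regression agreed with the t-test at 5% in 99.4% of 1,000 simulated trials.

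**The case against.** The strongest reply is that logistic regression does not have to mean dichotomising. A proportional-odds model uses the ordered score, and a model with arm as the dependent variable uses the score as a predictor. Neither needs a threshold, and step 7 shows that the second would almost always repeat the t-test. This stands, so it would be wrong to say that the protocol forces a yes/no cut. What remains is that the protocol states neither form, and the unqualified term, used to compare an outcome between arms, ordinarily means a binary outcome.

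Secondly, a reader might infer that the SF-36 comparison loses power, from 80% to about 60% or less. The text does not support that. It keeps the t-test, and the loss arises only if a dichotomised analysis replaces it or is allowed to decide. Under the sentence as written, the cost is possible conflict and a modest rise in false positives.

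Thirdly, a reader might infer that the regression was meant for bleeding and was attached to the SF-36 by mistake. Nothing shows this. Chi-square is a sound test for a binary outcome in a 1:1 randomised trial, and the word that opens the bleeding analysis as the first step leaves room for more.

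Finally, the model form and the ranking of secondary analyses could be left to a SAP that is not shown. That is fair for the details. It does not cover a mismatch between method and outcome that the protocol itself fixes. Inter-quartile ranges beside a test are ordinary description and no fault in themselves.

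**Conclusion.** The point holds in a limited form and is minor. One of the two analyses named for the SF-36 does not fit the outcome on its ordinary reading, no threshold is defined, and no rule says which analysis decides.

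If the score is dichotomised, the analyses disagree at 5% in about a quarter of trials with a median cut, and an either-test rule has a false-positive rate of about 7.5-7.9%. The drop in power to roughly 59-62% or 52-53% applies only if the dichotomised analysis is the deciding one.

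All these sizes rest on normal scores, 77 per arm, complete follow-up and, except for the false-positive rate, a difference of 0.45 SD. The cuts are illustrations, since the protocol gives none. Skewed or bounded SF-36 scores would change the sizes but not the undefined outcome or the missing rule. The primary bleeding analysis and the total of 154 do not depend on any of this.

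**What to change.** Replace the SF-36 sentence in Data Handling with:

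> SF-36 scores at 3 months will be compared between arms by the t-test (equivalently, linear regression of the score on arm), reporting the mean difference with 95% CI; this is the deciding analysis. Medians and inter-quartile ranges are descriptive, and a Wilcoxon test will be reported as a sensitivity analysis whatever the distribution.

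Delete logistic regression for the SF-36. If the sponsor wishes to keep it, label it supportive only and fix its form in advance, for example proportional odds. The Wilcoxon test should be unconditional: a rule that switches tests if scores look skewed would bring back a choice made after seeing the data.

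The cost is one sentence, made before unblinded data are analysed. It needs no extra patients or data collection and leaves the sample size as it is. The only thing given up is an unplanned yes/no presentation of the SF-36.

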#### Time frame

Based on the current volume of hysterectomies for the Minimally Invasive Surgery Division at Texas Tech, we expect to enroll 3 patients per week on average. We expect the data collection phase to span approximately 72 weeks (Taking into account the 3 month waiting period before the final satisfaction survey on the last patient enrolled). Data analysis will span an additional 12 weeks.

## Strength/Innovation

Postoperative vaginal bleeding is one of the most common complaints after hysterectomy, and its negative impact on patient satisfaction has been demonstrated. Furthermore, if these symptoms prompt phone-calls to the office, nurse-visits, or a trip to the emergency department, valuable health-care resources are utilized. Although the technique of closing apexes separately is considered a standard variation, its impact on outcomes has never been evaluated in a controlled prospective fashion, where standardized surveys are given to patients to determine impact. The results from this trial will help surgeons determine the best technique for re-approximating the vaginal cuff after hysterectomy.

## Limitations

The main confounding factors when comparing surgical techniques are difference in operating style between surgeons and baseline surgical characteristics (large uteri that may require more dissection and tissue manipulation, etc.). To control for this we are only recruiting patients from 3 surgeons who have a similar operating technique. In addition to this, we are documenting operating time and specimen weight, which can be used to compare both groups and assure that they are homogenous to these potential confounders. Baseline patient characteristics that can influence postoperative healing, such as diabetes and steroid use will also be accounted for. Post-hoc analysis will also be made specifically stratifying the data based on these characteristics.

#### **Risks / Safety**

There are no known risks associated to either method of vaginal cuff closure. Both are common variations that have been utilized throughout the country for several years. We are attempting to determine if one of the two methods has a higher risk of postoperative bleeding. To date, this has not been answered. We will have an assigned safety monitor that will perform an interim analysis of the cohort after every 20 subjects are enrolled. If the experimental arm demonstrates an increase of greater than 10% in visits to the emergency-room related to post-operative complaints, or an increase in unexpected complications (wound infection, wound dehiscence, etc.), the study will be halted.

There is also the potential risk of accidental disclosure of the health information that will be collected. To mitigate this, all stored data will be de-identified in a secure server using TTUHSC approved software (Red-Cap) that can only be accessed by members of the research team.

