#### Spanish version:

En una escala del 0-10, con 0 siendo nada de dolor, y 10 siendo el peor dolor posible, ¿Qué número representaría su dolor pélvico/vaginal en este momento?

0 1 2 3 4 5 6 7 8 9 10

En los 6 meses antes de su cirugía, se considera sexualmente activa?

Si No

¿Ha tenido sangrado vaginal o manchado después de su cirugía? (Sin contar los primeros dos días después de la operación)

Si	No									
	Si la respue	sta fue sí, ¿con q	ue frecuencia	?						
	Diario	La mayoría d	e los días	Infrecuente						
	¿Cómo des	¿Cómo describiría su sangrado?								
	Solo al ir al baño		Manchado	durante el día	Más que manchado					

# ANNEX 3

English Version										
Have you experienced vaginal bleeding in the last 2 weeks?										
Yes		No								
Have you had vaginal intercourse since your surgery?										
Yes		No								
If yes, rate from 0-10 how painful the last time you had intercourse was? With 0 being no pain and 10 being the worst pain ever										
0	1	2	3	4	5	6	7	8	9	10
Have you been to the emergency department after your surgery for any related surgical problems?										
Yes		No								
Spanisł	n Versior	ı								
¿Ha tenido sangrado vaginal en las últimas 2 semanas?										
Si		No								
¿Ha tenido relaciones sexuales vía vaginal desde su cirugía?										
Si		No								
Si la respuesta fue sí, en una escala del 0 al 10, con 0 siendo nada de dolor y 10 siendo el peor dolor posible, ¿Cuánto dolor tuvo durante la última vez que tuvo relaciones sexuales?										
0	1	2	3	4	5	6	7	8	9	10
¿Ha tenido que visitar el departamento de urgencias desde su cirugía, por problemas relacionados a la operación?										

Si No

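### The safety looks come after every 20 subjects enrolled, but the emergency-room and postoperative complication data they act on are scheduled only about 3 months later, and no chart check is timed to the looks.

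*Protocol*

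**What the plan says.** **Looks and halt rule (Protocol, Risks / Safety).** "We will have an assigned safety monitor that will perform an interim analysis of the cohort after every 20 subjects are enrolled". The rule has two limbs. The first reads "If the experimental arm demonstrates an increase of greater than 10% in visits to the emergency-room related to post-operative complaints". The second continues "or an increase in unexpected complications (wound infection, wound dehiscence, etc.), the study will be halted".

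**When the events are collected (Protocol, Methods).** "A retrospective chart review will also be performed 3 months after enrollment to evaluate for any postoperative visits to the emergency department"; the same sentence adds re-admissions, re-operations and infections. Data Handling describes the review this way: "Using the master key, we will perform a retrospective chart review to complete final data points". It also limits access to the master key to the principal investigator. The patient's own report comes by telephone: "Between 90-114 days after surgery, patients will be called by a member of the research team". The relevant item is in Annex 3: "Have you been to the emergency department after your surgery for any related surgical problems".

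**What is collected earlier.** Annex 1, completed by the surgeon after the operation, records times, blood loss, lacerations and complications during cuff closure. Annex 2, given at the day 10-20 visit, asks about pain, sexual activity before surgery and bleeding. It has no emergency-department or complication item. Under Exclusion Criteria, an injury during cuff closure is recorded and goes to the safety officer.

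**Accrual (Protocol, Time frame).** "we expect to enroll 3 patients per week on average". Data collection is expected to last about 72 weeks, including the 3-month wait for the last patient.

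**The concern.** The looks are counted by enrolment, while the data they depend on follow a calendar delay of about 13 weeks or more. At the stated accrual a look falls due every 6.7 weeks, so two looks fall due within about the time one subject needs to reach the scheduled collection. A monitor who relied on that collection would have almost nothing to compare at the first two looks. A finding of no excess could then mean only that nothing had yet been gathered.

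A smaller ambiguity adds to this. Patients consent in the office before surgery, but allocation takes place after the hysterectomy and before cuff closure. If enrolment means consent, some subjects counted toward a look may not yet have been operated on or randomised.

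What is at stake is the usefulness of the early safety reviews. The sample size, primary outcome and primary analysis are not affected.

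**Working it through.** The protocol gives no figure for how many subjects contribute data at a look, so there is none to reproduce. The count follows from its own inputs.

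**Inputs**
- Looks at 20, 40, …, 140 enrolled: seven before the planned 154 (Risks / Safety; Sample Size).
- Accrual r = 3 per week (Time frame).
- Lag L = 3 months, taken as 13 weeks (chart review), or up to 114/7 = 16.3 weeks (Annex 3 call). The call is timed from surgery; surgery is assumed to follow enrolment promptly.

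**Formulas**
- Week of a look = enrolled / r.
- Subjects pending = r × L.
- Subjects with scheduled data = max(0, enrolled − r × L).

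**Central case:** r × L = 3 × 13 = 39 pending.

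| Look | Enrolled | Week | With scheduled data |
|---|---|---|---|
| 1 | 20 | 6.7 | 0 |
| 2 | 40 | 13.3 | 1 |
| 3 | 60 | 20.0 | 21 |
| 4 | 80 | 26.7 | 41 |
| 5 | 100 | 33.3 | 61 |
| 6 | 120 | 40.0 | 81 |
| 7 | 140 | 46.7 | 101 |

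**Sensitivity.** At 3 per week, accrual takes 154/3 = 51.3 weeks, and with a 13-week wait the total is 64.3 weeks. The stated 72 weeks therefore allows slower accrual: 154/(72 − 13) = 2.6 per week, or 154/(72 − 16.3) = 2.8 per week if the last contact is at day 114.

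| Rate per week | Lag (weeks) | Pending | With data at looks 1, 2, 3 |
|---|---|---|---|
| 3.0 | 13 | 39 | 0, 1, 21 |
| 3.0 | 16.3 | 49 | 0, 0, 11 |
| 2.6 | 13 | 34 | 0, 6, 26 |
| 2.8 | 16.3 | 45 | 0, 0, 15 |

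The number pending runs from 34 to 49, capped at the number enrolled. In every case look 1 has no subject with scheduled data, and look 2 has between 0 and 6 of 40.

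**What earlier collection would give.** Suppose looks are counted by randomisation, at 3 per week, and the data are taken at the postoperative visit, at latest day 20. Then 3 × 20/7 = 8.6 subjects are pending. About 11 of 20 would contribute at look 1 (20 − 8.6 = 11.4), about 31 of 40 at look 2 and about 51 of 60 at look 3.

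**The case against.** The best reply is that the protocol does not confine the monitor to the 3-month review. That review is described as completing final data points. Emergency visits and infections enter the chart when they happen, every patient meets the physician at day 10-20, and nothing bars an earlier chart check. A monitor's data source is also often set out in another document.

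Much of this stands. The events may well be available in the chart, and the weakness lies in the collection the protocol describes. But the protocol itself fixes the look schedule, the halt rule and the collection times, and these do not fit together. It describes no chart check at a look, and the master key needed for chart review is held by the principal investigator alone. The early route therefore has to be written in.

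Four stronger readings are tempting, and the document does not support them:

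- **That no harm could trigger a halt at the first look.** Annex 1 records cuff-closure complications on the day of surgery, and the complication limb of the rule is open-ended.
- **That these looks are the only safeguard.** The safety officer separately reviews injuries during cuff closure. That review does not cover emergency visits or wound events, however.
- **That later looks water down a true excess below the 10% threshold.** This requires unreviewed subjects to be counted as event-free and the 10% to mean percentage points. The protocol states neither. On a relative reading, equal dilution in both arms would cancel.
- **That a wait between consent and surgery makes the chart-review counts worse.** The review is timed from enrolment, so the counts stay the same; the wait only shortens the postoperative period covered.

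**Conclusion.** The point holds as a mismatch within the protocol. Followed as written, the scheduled collection leaves the first two looks essentially empty for emergency visits and postoperative complications (0 of 20 and about 1 of 40), and the third with about a third of its subjects (21/60 = 35%). From the second look on, about 39 subjects are pending, with the range shown above. These figures assume steady accrual and 3 months taken as 13 weeks. They describe scheduled collection only, and do not show that events would go unnoticed in routine care.

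This should be fixed, but it does not undermine the trial. The protocol describes both closures as common variations with no known added risk, and the efficacy analysis is untouched.

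**What to change.** Amend Risks / Safety as follows, leaving the halting thresholds as they are:

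1. Before each look, check the charts of all subjects randomised to date for the events the halt rule names, and state who does this, given the restriction on the master key.
2. Count looks by subjects randomised (envelope opened), not by subjects enrolled.
3. Compare the arms using only subjects whose charts have been checked and who have reached a stated minimum postoperative follow-up, for example the day 10-20 visit. Report the length of follow-up by arm. Without such a minimum, a subject operated on the day before would count as event-free.
4. Add the Annex 3 emergency-department question to Annex 2. The wording already exists in English and Spanish.

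Keep the 3-month chart review as the final data point.

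The cost is a wording amendment, one extra survey line in each language, and a brief chart check at each of seven looks. Some charts will be opened more than once. No extra patients or visits are needed.
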